### **List of Abbreviations**

*All abbreviations used throughout the protocol must be defined.*

AE	Adverse Event
AUC	Area Under the Curve
cfRNA	Cell free RNA
BMI	Body Mass Index
CFR	Code of Federal Regulations
Cr	Creatinine
CrCl	Creatinine Clearance
CRF	Case Report Form
DBP	Diastolic Blood Pressure
DSMB	Data Safety Monitoring Board
DSMP	Data Safety Monitoring Plan
FDA	Food and Drug Administration
FE	Fractional excretion
GA	Gestational Age
GCP	Good Clinical Practice
GFR	Glomerular filtration rate
HIPAA	Health Insurance Portability and Accountability Act of 1996
HRBFA	Human Research Billing Analysis Form
ICF	Informed Consent Form

WCM IRB Protocol #: 1809019585

NYP-Q IRB Protocol : #14540722

Version Date: 01/29/2025

IND	Investigational New Drug
IRB	Institutional Review Board
NIH	National Institutes of Health
NMR	Nuclear Magnetic Resonance
PE	Preeclampsia
PHI	Protected Health Information
PRA	Plasma Renin Activity
PTH	Parathyroid Hormone
PI	Principal Investigator
REDCap	Research Electronic Data Capture
ROC	Receiver Operating Characteristic
SAE	Serious Adverse Event
SAS	Statistical Analysis Software
SBP	Systolic Blood Pressure
SPE	Superimposed preeclampsia
SUSAR	Suspected Unexpected Serious Adverse Reaction
UAP	Unanticipated Problem
WCMC	Weill Cornell Medical College

### Protocol Summary

Full Title:	A Randomized Controlled Trial Comparing Low Doses Of Aspirin In The Prevention Of Preeclampsia (ASAPP)
Short Title:	ASAPP
Clinical Phase:	III
Principal Investigator:	[name]
Sample Size:	N= 400 which may be modified after the first stage of our study
Accrual Ceiling:	400
Study Population:	Pregnant women < 16 weeks of gestation at high risk of PE (preeclampsia in a prior pregnancy, multifetal gestation, chronic hypertension, Type 1 or 2 diabetes, renal disease, autoimmune disease).
Accrual Period:	5 years
Study Design:	Open-label, randomized clinical trial. First stage: pilot to determine feasibility and sample size and second stage: completing the clinical trial
Study Duration:	9 months for each patient (from recruitment until 6 weeks postpartum)
Intervention Description:	Randomized to 81mg vs. 162mg of aspirin per day
Primary Objectives:	To compare the incidence of preterm PE and PE with severe features in women treated with 81mg to those treated with 162mg of aspirin per day.
Secondary Objectives:	

Evaluate and compare the adherence of pregnant women to 81 mg and 162 mg of daily low-dose aspirin using a validated, Simplified Medication Adherence Questionnaire (SMAQ).

Compare maternal and fetal outcomes in pregnant women at a high risk for preeclampsia who are treated with either 81 mg or 162 mg of daily aspirin during pregnancy, including preeclampsia <math>\geq</math> 37 weeks, severe maternal hypertension, preterm delivery, fetal growth restriction, placental abruption and maternal/fetal mortality.

To compare the time-to-event for developing PE for women treated with 81mg vs. 162mg of aspirin per day.

To assess the adherence to low dose aspirin in pregnant women that are a high risk for preeclampsia and compare adherence rates for women on 81mg vs 162mg of aspirin per day.

Exploratory Objectives:	To assess the impact of specific co-morbidities (diabetes, chronic hypertension, renal disease and autoimmune disease), blood pressure

*control, age and race on the relationship between treatment group and PE incidence.*

*To compare cfRNA profiles of the 2 treatment groups (81mg vs. 162mg aspirin per day) and of pre-treatment samples in order to better understand how ASA initiation and dosing affect the transcriptome of pregnancy in women who develop PE and in those who do not*

**Endpoints:** *Incidence of PE, gestational age at onset of PE*

**SCHEMA**

Subjects screened for eligibiliy from the New York Presbyterian  
– Weill Cornell/Queens affiliated Obstetric Clinics and The  
Hypertension Center

Patient consented for participation

Randomization to either:

Arm 1: Subjects will be given 81mg ASA daily.

Arm 2: Subjects will be given 162mg ASA daily.

Evaluation at:

Baseline visit (<16 weeks)

18-22 weeks

24-28 weeks

34-38 weeks

Delivery

Postpartum

Determination of pregnancy outcomes and of study  
endpoint for each patient

Upon completion of the study: data anlysis and  
interpretation of study results

## 1. STUDY OBJECTIVES

### 1.1. Primary Objective

Compare the incidence of preterm (<37 weeks) preeclampsia and preeclampsia with severe features (American College of Obstetricians and Gynecologists [ACOG] 2019 definition (1)) in high risk pregnant women treated with either 81 mg or 162 mg of daily aspirin during pregnancy

### 1.2. Secondary Objectives

- Evaluate and compare the adherence of pregnant women to 81 mg and 162 mg of daily low-dose aspirin using a validated, Simplified Medication Adherence Questionnaire (SMAQ).
- Compare maternal and fetal outcomes in pregnant women at a high risk for preeclampsia who are treated with either 81 mg or 162 mg of daily aspirin during pregnancy, including preeclampsia  $\geq$  37 weeks, severe maternal hypertension, preterm delivery, fetal growth restriction, placental abruption and maternal/fetal mortality.
- To compare the time-to-event for developing PE for women treated with 81mg vs. 162mg of aspirin per day.
- To assess the adherence to low dose aspirin in pregnant women that are a high risk for preeclampsia and compare adherence rates for women on 81mg vs 162mg of aspirin per day.

### Exploratory Objective:

- To assess the impact of specific co-morbidities (diabetes, chronic hypertension, renal disease and autoimmune disease), blood pressure control, age and race on the relationship between treatment group and PE incidence.
- To compare cfRNA profiles of the 2 treatment groups (81mg vs. 162mg aspirin per day) and of pre-treatment samples in order to better understand how ASA initiation and dosing affect the transcriptome of pregnancy in women who develop PE and in those who do not

## 2. BACKGROUND

### 2.1. Preeclampsia

#### 2.1.1 Preeclampsia, risk reduction with low-dose aspirin

Preeclampsia (PE) is a serious and potentially fatal complication of pregnancy. It is a placental disease characterized by an elevated blood pressure in the 3rd trimester with multisystem involvement (proteinuria, elevated liver enzymes, low platelet count and/or neurologic symptoms). PE can cause pulmonary edema, seizures, or stroke and is a leading cause of maternal mortality. The pregnancy outcomes are further worsened if PE develops before term (2, 3). Women who have a history of PE in a

prior pregnancy, diabetes, preexisting hypertension, kidney disease, multifetal gestation or autoimmune diseases are at an increased risk to develop PE in a subsequent pregnancy (4).

Clinical trials evaluating the benefits of low-dose aspirin (ASA) have used a wide range of doses from 60mg to 150mg orally daily with low-dose being defined as less than 325mg per day. Taking ASA (as opposed to placebo) is thought to reduce the risk of preeclampsia by 17%, without increasing the risk of major obstetric bleeding. The number needed to treat is only 19 women (1). ASA is currently the only prophylactic therapy for PE in high-risk women to be recognized by the US Preventive Task Force and should be initiated early in the second trimester of pregnancy, before 16 weeks of gestation (4).

There has also been more awareness that the efficacy of ASA in preventing preeclampsia is limited by the poor adherence of patients to this therapy. Indeed, a cross-sectional study has estimated that up to 46% of women (n=42) on ASA therapy may not be compliant to it, as determined by a validated Simplified Medication Adherence Questionnaire (SMAQ) (5). Adherence is essential to the efficacy of ASA in preventing preterm preeclampsia (6). It would therefore be of interest to obtain more information about adherence to ASA in women who need this therapy.

### 2.1.1 Molecular basis of aspirin in preeclampsia risk reduction

The molecular basis for the protective effect of ASA in pregnancy is still a matter of debate (7). Cell free RNAs (cfRNAs) have recently been identified as promising biomarkers for preterm birth in pregnant women. Indeed, a panel of 9 placental cfRNAs (CGA, CAPN6, CGB, ALPP, CSHL1, PLAC4, PSG7, PAPPA and LGSALS14) were found to accurately predict gestational age at delivery in a cohort of 38 women (8). CfRNA profiling enables the detection of placenta-specific cfRNA in the maternal peripheral blood and can therefore give us a unique, non-invasive, insight into placental health (9). Presently, the molecular effect of ASA on cfRNA profiles in pregnancy has not been described. It is also unknown if ASA dosing or the development of PE affect cfRNA profiles.

In addition to testing our hypothesis that 162mg of ASA daily may be associated with lower incidence of PE than 81mg; our study would serve as a platform to collect and biobank samples (urine and blood). These samples would be invaluable in determining the molecular basis of PE development and the differential effects of ASA doses in PE prevention. Biobanked samples will be used (funding permitting) for cfRNA profiling but may also be used for proteomic, transcriptomic, metabolomic or cell-typing analysis if future promising hypotheses emerge.

### 2.1.3 What don't we know?

The current literature is lacking in evidence to recommend a specific daily dose of ASA. Recent meta-analyses (10, 11) have suggested that there may be a dose response in the protective effect of ASA for PE. As compared to 60mg per day, an ASA dose of 100mg per day was associated with a lower relative risk of PE (0.44 vs 0.57, p=0.36) (10). A large study of 1776 women has compared a slightly

higher dose of ASA (150mg per day) to placebo and found a decrease in preterm delivery (before 37 weeks) due to PE (OR 0.38, p=0.004) (12). Meta-analyses have shown that any dose of ASA above 60mg per day is protective and should be used to prevent PE in high risk pregnancies (3, 4).

To date, there has not been any studies comparing lower doses of ASA (such as 81mg, the traditional “baby aspirin” dose sold in the US) to higher “low-dose” ASA regimens (such as 162mg) in their ability to prevent preterm or severe PE in women who are at a high risk for this devastating disease.

## **2.2 Rationale**

PE is a morbid and potentially lethal complication of pregnancy and is more common in women with specific risk factors. ASA is currently the only prophylactic therapy for PE in high-risk women to be recognized by the US Preventive Task Force and should be initiated early in the second trimester of pregnancy, before 16 weeks of gestation (4). However, currently there is no literature comparing various low-dose aspirin formulations in the risk reduction of PE. In the United States, the currently available low-dose aspirin is over the counter and is found in 81mg tablets. Therefore, when clinicians initiate therapy with low dose ASA, they may prescribe 1 or 2 tablets of 81mg ASA per day depending on personal preference cannot be assisted by evidence to guide their decision.

The proposed study would determine the incidence of preterm PE or preeclampsia with severe features in women taking either 81mg or 162mg in a randomized setting, from two centers (Weill Cornell/New York Presbyterian and New York Presbyterian Queens). We hypothesize that the information gained from this trial will permit a more accurate sample size calculation for a larger clinical trial powered to accept or reject our testing hypothesis.

If our hypothesis is rejected and 162mg of daily ASA is not associated with a lower incidence of severe or preterm PE in pregnancy compared to 81mg, this may be due to lack of power to detect a smaller effect. We would then evaluate the feasibility and results and determine whether a larger trial is reasonable.

cfRNAs may provide further insight into the pathophysiology of the protective effect of ASA on the development of PE in high risk women. Assessing molecular pathways in the development of PE may allow opportunity for earlier diagnosis, specific triaging of patients to closer monitoring and further development of preventative or curative treatment strategies.

## **2.3 Risk/Benefit Assessment**

There will be no direct benefit to the participants of this study, given the equipoise about which low dose of aspirin would be associate with better outcomes. We hope the information learned from this study will benefit other patients at risk for developing preeclampsia in the future.

Both our study arms are doses that are currently included in the standard of care. We do not therefore anticipate any added risk to routine care by being enrolled in the study. The risks that have been associated with aspirin in routine clinical care include a slight increase in minor bleeding but no

increase in major bleeding (requiring intervention) (3, 4).

Patients may experience discomfort and bruising at the site of the needle stick. Lab work will be drawn at the initial screening visit and at 18-22 weeks, 24-28 weeks and 34-38 weeks gestation.

Another potential risk to participating in the study would include loss of confidentiality and will be avoided as described in following sections (i.e. section 11. Data reporting/regulatory considerations and, section 13. Data and safety monitoring plan).

### **3. SUBJECT SELECTION**

#### **3.1 Study Population**

Our study population will include pregnant adult women, less than 16 weeks pregnant that are seen at a New York Presbyterian – Weill Cornell affiliated Obstetric or Hypertension Clinic and are at a high risk for preeclampsia (see section 3.2. for inclusion criteria) who thus meet criteria for low dose aspirin therapy. Subjects will be screened for eligibility from the New York Presbyterian – Weill Cornell and Queens campuses' affiliated Obstetric Clinics and The Hypertension Center by reviewing the list of patients scheduled to be seen at that clinic. Eligible patients will be approached by research staff if deemed acceptable by their clinical provider. Patients who consent to being in the study will be enrolled.

Clinical data in addition to urine and venous peripheral blood will be collected from pregnant women,  $\geq 18$  years old, with at least one of the following risk factors for developing PE.

#### **3.2 Inclusion Criteria**

Major Inclusion Criteria:

Pregnant patients,  $\geq 18$  years old, at less than 16 weeks' gestation (as documented by ultrasound) with at least one of the following risk factors for developing PE:

- PE in a prior pregnancy
- Chronic hypertension (prior to pregnancy or before 20 weeks' gestation)
- Type 1 or 2 diabetes
- Renal disease (proteinuria  $\geq 300$ mg/day or estimated GFR $<90$ mL/min/1.73 m^2)
- Multifetal gestation
- Autoimmune disease (e.g. systemic lupus erythematosus, antiphospholipid syndrome)

#### **3.3 Exclusion Criteria**

Major Exclusion Criteria:

- Patient with known intention to terminate pregnancy

- Major fetal malformation seen on ultrasound
- Contraindication to ASA therapy (including but not limited to allergy and high bleeding risk)

## 4. REGISTRATION PROCEDURES

### 4.1 Patient Registration

Screening will take place at the Women's Health Practice, located at [name], New York Presbyterian Queens ([name]) and its affiliated high risk clinics, Weill Cornell Maternal Fetal Medicine, located at [name] and The Hypertension Center, located at [name]. Patient will be registered with Weill Research Gateway as per IRB/JCTO protocol.

## 5. STUDY PROCEDURES

Study visits will take place at the Women's Health Practice, located at [name], Weill Cornell Maternal Fetal Medicine, located at [name], New York Presbyterian Queens ([name]) and its affiliated high risk clinics, and The Hypertension Center, located at [name].

During the study, **as a part of standard prenatal care**, participants will be requested to have their blood pressure checked at each visit. In addition, lab work will be drawn at the initial screening visit and at 18-22 weeks, 24-28 weeks and 34-38 weeks gestation. If patients are scheduled to have their blood drawn for clinical purposes on that day, we will not perform an additional needle stick.

Data collection will be done through a secure RedCap database. Bio samples will be stored in a de-identified manner in the Nephrology research lab ([name] lab) in [name].

## 5.1 Schedule of Evaluations

	Baseline Visit (<16 weeks)	Week 18-22 Visit	Week 24-28 Visit	Week 34-38 Visit	Study outcome	Delivery	Postpartum Visit
Performed by study personnel at study visits							
Informed consent	X						
Demographics	X						
Randomization	X						
Physical exam	X	X	X	X			X
Vital signs	X	X	X	X			X
Medication list	X	X	X	X			X
Adherence Questionnaire		X	X	X			
Obtained from chart review of information collected as part of standard clinical care							
Medical history	X						
Vital signs	X				X	X	
Physical exam	X				X	X	
CBC w/diff, platelets	X	X	X	X	X	X	X
Serum chemistry a	X	X	X	X	X	X	X
Urine studies b	X	X	X	X	X	X	X
Fetal testing results	X	X	X	X		X	X
Placental pathology report						X	
Operative and birth reports						X	
Neonatal records						X	
Outcome Evaluation (PEC)		X-----					X
Adverse event evaluation	X-----						X

a: Albumin, bicarbonate, BUN, chloride, creatinine, glucose, potassium, AST, ALT, sodium, uric acid and lactate dehydrogenase

b: Urinalysis, urine chemistry, urine protein, urine creatinine, urine albumin.

## 5.2 Treatment groups

At the initial visit, participants will be consented then randomized using the RedCap software to either Arm 1: 81mg ASA per day or Arm 2: 162mg ASA per day.

Adherence will be ascertained by questionnaire including a validated questionnaire: the simplified medication adherence questionnaire (SMAQ) (5).

Once funding can be obtained, we may further evaluate adherence by quantifying Thromboxane metabolite excretion in the collected and stored urine samples (urine samples will be stored in our BioBank at the Nephrology lab [[name] lab, [name]]). This method has previously been used in pregnancy to determine ASA activity/adherence (13, 14).

The patients will then be monitored throughout pregnancy for side effects, study endpoints and clinical data will be collected as described in section 5.1. Delivery records and postpartum course will also be considered to rule out delivery/postpartum complications including obstetric hemorrhage and postpartum PE.

- Renal Insufficiency: serum creatinine  $>$  1.1 mg/dl or doubling of serum creatinine
- Impaired liver function: elevated transaminases to twice normal

- Pulmonary edema
- New onset headache that does not respond to medication and that cannot be attributed to another etiology
- Changes in vision

Adverse event monitoring will be conducted throughout the course of the study and will be assessed at each visit. Adverse events will be reported to the IRB as indicated by their regulations.

#### **5.4. Biobanking and cfRNA profiling**

Blood and urine collected as per section 5.1 will be stored in our BioBank at the Nephrology lab ([name] lab, [name]). These samples would be used for future investigations of biomarkers of PE and for changes associated with different doses of ASA.

Once funding can be obtained, we will proceed with profiling of cell free mRNA in the collected plasma samples in order to investigate whether, in pregnant women at a high risk for PE, cfRNA profiles can anticipate PE or predict the ability of bASA to prevent (or not) this disease. The profiling of cfRNA will be done in collaboration with [name] [name] (Cornell Ithaca).

##### Next generation sequencing.

cfRNA will be isolated from 1ml plasma according to a published protocol (8). We will use a Plasma/Plasma Circulating RNA and Exosomal Purification kit (Norgen, cat 42800) for RNA extraction. DNA contamination will be removed by Baseline-ZERO DNase (Epicentre) followed by RNA Clean and Concentrator-5 kit (Zymo). Library preparation will be performed using SMARTer Stranded Total RNAseq-Pico Input Mammalian kit (Clontech). cfRNA sequencing will be done using an Illumina based platform. Sequencing output will be processed through an in-house pipeline. cfRNA indicative of PE will be identified using the edgeR software by performing an exact test, a likelihood ratio test, and quasi-likelihood F-test.

##### Absolute quantification of cell-free RNAs using real time quantitative PCR assays (QPCR).

We will reverse transcribe the RNA isolated from the plasma samples to cDNA using the CellsDirect One-Step RT-qPCR kit (Thermo-Fisher) together with a pool of 96 primer pairs. If an informative cfRNA discovered by deep sequencing is not included in the standard primer/probe pool, we will design a specific primer/probe for the reverse transcription and preamplification of that cfRNA. A 20-cycle preamplification will then be done in Veriti® thermal cyclers. We will use Applied Biosystems' QuantStudio™ 7 Flex Real-Time PCR System for the absolute quantification of the cfRNAs discovered to be prognostic of PE at a false discovery adjusted p-value <0.01. The PCR reaction for each sample will be set up in duplicate.

##### Statistical analysis for cfRNA profiling:

Standard descriptive statistics (such as mean or median, range and percentage) will be computed for patient characteristics. Receiver-operating-characteristic (ROC) curve analysis of levels of cfRNAs will be performed and used to determine area under the curve (AUC) as the discrimination statistic, and the cutoff point that yields the highest combined sensitivity and specificity (Youden's index) for predicting PE vs. no PE. Logistic regression analysis with stepwise backward elimination will be used to develop parsimonious prognostic signatures based on linear combinations of cell-free RNAs and to compute the resulting AUC. Models will be

compared with likelihood ratio test (for nested models) and internally validated by 10-fold cross validation. Genes with an effect size threshold of 0.8 between the PE and No PE groups, and with false discovery rate (FDR) of 0.05 will be considered significantly different (8).

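### The cfRNA analyses contrast only PE with no PE, so as written they give no result on aspirin dose or initiation, and the prediction analysis has no rule on which samples are eligible

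*Combined protocol and SAP*

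**What the plan says.** The Protocol Summary and the Exploratory Objective in section 1 give the aim: "To compare cfRNA profiles of the 2 treatment groups (81mg vs. 162mg aspirin per day) and of pre-treatment samples", to learn what starting aspirin and its dose do to the transcriptome in women who develop PE and in those who do not. Section 5.4 adds a second aim, to learn whether "cfRNA profiles can anticipate PE or predict the ability of bASA to prevent (or not) this disease".

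The cfRNA analyses appear only in section 5.4:

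- Next generation sequencing: "cfRNA indicative of PE will be identified using the edgeR software". Three tests are listed (exact, likelihood ratio, quasi-likelihood F), with no design or covariates.
- Quantitative PCR: the transcripts carried forward are those found prognostic of PE.
- Statistical analysis for cfRNA profiling: ROC curves with a cut-off at the "highest combined sensitivity and specificity (Youden's index) for predicting PE vs. no PE"; backward logistic regression to build "parsimonious prognostic signatures based on linear combinations of cell-free RNAs", with 10-fold cross-validation; and a gene-level rule, "Genes with an effect size threshold of 0.8 between the PE and No PE groups, and with false discovery rate (FDR) of 0.05".

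Section 12.5, the trial's other analysis section, does not mention cfRNA.

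On sampling, section 5 gives four draws: the initial visit (before 16 weeks), then 18-22, 24-28 and 34-38 weeks. Section 5.4 defines the banked samples by reference to section 5.1, where the laboratory rows are also ticked for the study outcome, delivery and postpartum visits.

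**The concern.** An analysis that contrasts PE with no PE yields transcripts that differ by PE status. It does not estimate a difference between doses or a change after aspirin is started, and those are the stated objective.

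The second problem concerns prediction. A signature that anticipates PE has to be built on samples taken before PE. Without a rule on visit or onset, samples from women who already have the disease can enter the ROC and logistic models, and cases and non-cases can differ in gestational age at sampling. Either could make a marker with no predictive value look prognostic. Leaving the rule open also means that the visit, the samples and the test could be chosen after results are seen.

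**Working it through.** The cfRNA plan states no sample size, power or expected AUC, so there is no figure to reproduce. The check sets the aims beside the analyses, then asks which samples could enter.

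**1. Aim against analysis**

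| Stated aim | Term needed | In section 5.4 |
|---|---|---|
| 81 mg versus 162 mg | treatment arm | none |
| Pre-treatment versus later samples | change from baseline within woman | none |
| Both, by PE status | PE-by-visit and arm-by-PE-by-visit | none |
| Anticipate PE | PE versus no PE in pre-onset samples | contrast given, sample rule absent |

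Two of the three edgeR tests can carry covariates and blocking; the exact test is a two-group comparison and cannot. No covariates are named for any of them.

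**2. Which samples could be drawn after onset**

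- Onset before 34 weeks, still pregnant at the last visit: the 34-38 week sample is post-onset.
- Onset before 34 weeks, already delivered: no 34-38 week sample exists. It cannot contaminate, but the woman's samples then come from earlier gestations.
- Onset from 34 to under 37 weeks: the sample may fall on either side of onset.
- Term PE, which also counts as PE in this contrast: the 34-38 week sample can be pre-onset.
- Study outcome, delivery and postpartum: any sample banked there from a woman with PE would usually be at or after onset. Those laboratory rows sit under chart review, so it is unclear whether research blood is taken at these visits. The 34-38 week draw raises the problem even if it is not.

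Section 12.1 expects some diagnoses between scheduled visits. No section removes later samples from the cfRNA analysis.

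**3. What post-onset samples could do (assumed inputs)**

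Let f be the share of case samples drawn after onset. Against a common set of control samples, pooled AUC = (1 − f) × AUC before onset + f × AUC after onset.

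| AUC before | AUC after | f = 10% | f = 25% | f = 50% |
|---|---|---|---|---|
| 0.50 | 0.80 | 0.53 | 0.575 | 0.65 |
| 0.50 | 0.90 | 0.54 | 0.60 | 0.70 |
| 0.60 | 0.90 | 0.63 | 0.675 | 0.75 |

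For example, 0.75 × 0.50 + 0.25 × 0.90 = 0.60. The documents give none of these inputs.

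**4. Gestational age**

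The last three windows are each 4 weeks wide (22 − 18, 28 − 24, 38 − 34). Baseline has no lower limit. Scheduled draws therefore span more than 38 − 16 = 22 weeks, and the logistic predictors are cfRNAs only.

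As an illustration, take a marker that rises 1 SD per visit and is unrelated to PE, with four visits pooled. The chance that a case sample from visit 1, 2, 3 or 4 exceeds a random control sample is 0.209, 0.395, 0.605 or 0.791.

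- All cases lack visit 4: (0.209 + 0.395 + 0.605) / 3 = 0.40.
- Half of the cases lack visit 4: (0.209 + 0.395 + 0.605 + 0.5 × 0.791) / 3.5 = 0.46.

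The true value is 0.50, so pooling alone can create a signal. The slope and the missing shares are assumptions.

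**5. Is baseline pre-treatment?**

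Section 12.2 starts therapy at the baseline visit, so the baseline draw is the candidate pre-treatment sample. Section 3.3 does not exclude women already taking aspirin, and section 2.3 places both doses within standard care. The section 5.1 medication list would identify such women, but no rule uses it.

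**The case against.** The strongest reply is that this is exploratory work, done only if funding is found, and that the missing detail can be written before sequencing. That stands as to weight: the primary comparison is untouched. It does not answer the point that the analyses which are written down omit the objective.

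Four stronger readings are tempting, and the documents do not support them.

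- **That all visits will be pooled.** A reader might compute 394 × 4 = 1,576 samples entering one contrast. The plan never says that visits are pooled or how many samples will be sequenced. The product is a ceiling on scheduled draws, and section 12.3 itself calls the calculation behind 394 approximate. What stands is that nothing prevents pooling.
- **That the AUC is inflated.** Post-onset sampling is possible, not certain, and the figures above rest on assumptions.
- **That these transcripts are known to vary with gestation.** The text of section 2.1.1 concerns gestational age at delivery; variation with gestation at sampling is suggested only by the title of the cited cfRNA study. Adjustment is a precaution, not a correction of a demonstrated bias.
- **That many baseline samples are already on treatment.** No section says how many women take aspirin before enrolment, so this merits a sensitivity step only.

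It is also fair to say that 10-fold cross-validation is already planned. What is not stated is whether gene selection, elimination and the cut-off are repeated inside each fold.

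**Conclusion.** The concern holds in two parts. First, and without any assumption, the cfRNA analyses as written contain no dose contrast and no pre-treatment contrast, so they cannot report on their own objective. The defect is in the analysis, not the design: the randomised arms and the baseline draw are there, and the data could support these comparisons once specified. Second, the prediction analysis lacks a visit window and an onset rule, so its AUC may include disease-state samples and differences in gestational age. The documents do not allow that effect to be sized. The point should be settled before sequencing; it does not bear on the trial's primary result.

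**What to change.** Revise the sequencing and statistical analysis parts of section 5.4.

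1. **Dose and initiation.** Replace the three edgeR tests with one quasi-likelihood model: woman as block, visit, arm-by-visit (change from baseline, 162 mg versus 81 mg), gestational age at sampling, and PE-by-visit and arm-by-PE-by-visit terms. Arm-by-visit is the randomised comparison. Contrasts by PE status condition on a post-randomisation outcome and should be labelled descriptive. So should the change from baseline common to both arms, because both start aspirin while gestation advances.
2. **Prediction.** Use one sample per woman per visit window, drawn before the recorded gestational age at PE onset. Analyse each window separately with gestational age at sampling as a covariate. Carry out gene selection, backward elimination and the Youden cut-off inside each cross-validation fold.
3. **Sensitivity.** Use the baseline medication list to limit the pre-treatment contrast to women not already taking aspirin.

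The cost is mainly drafting. Visits, arm and medication lists are already planned. Gestational age at onset is an endpoint in the Protocol Summary, but section 5.3 describes adjudicating the PE category and not its timing, so the sponsor should confirm that onset is recorded precisely enough to compare with draw dates. The prediction analysis will have fewer samples and probably a less favourable AUC.
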